#### Amend:

30-69% recruitment achieved. Potentially progress to main trial with additional sites being recruited as well as a screening log and protocol review, following discussion with Trial Steering Committee and HTA.

#### Stop:

Less than 30% recruitment achieved. The decision to progress will be made by the Trial Steering Committee in association with the HTA secretariat.

If the loss to follow-up (for those who have observed 6 months follow-up) exceeds 20%, without an identifiable and correctable reason it would not be feasible to progress to the substantive phase without substantial changes to the study design.

#### MAST-DURATION

Stage 1 aims to recruit approximately 50 patients within 12 months. If the progression rules are met, stage 2 will aim to recruit an additional 378 patients within a further 24 months. The expected average annual recruitment is 5-10 patients per site.

Progression criteria to the substantive phase

Go:

70-100% recruitment achieved. Progress to main trials following a review of screening logs and protocol. Any barriers for recruitment will be addressed.

#### Amend:

30-69% recruitment achieved. Potentially progress to main trial with additional sites being recruited as well as a screening log and protocol review, following discussion with Trial Steering Committee and HTA.

# Stop:

Less than 30% recruitment achieved. The decision to progress will be made by the Trial Steering Committee in association with the HTA secretariat.

If the loss to follow-up (for those who have observed 6 months follow-up) exceeds 20%, without an identifiable and correctable reason it would not be feasible to progress to the substantive phase without substantial changes to the study design.

If either the DURATION or PROPHYLAXIS trial fails to recruit to target and subsequently doesn't proceed to stage 2, then recruitment to the other trial will continue under this protocol as appropriate.

## 8.4 Participants Trial Duration

#### MAST-PROPHYLAXIS

Trial duration will be approximately 24 months, consisting of a 7 day treatment period followed by a 14 day, 6 month, 12 month, 18 month and 24 month follow up.

# MAST-DURATION

Trial duration will be approximately 24 months, consisting of either up to 3 months or at least 6 months treatment with a 6 month, 12 month, 18 month and 24 month follow up.

# 8.5 Trial Objectives

## 8.5.1 MAST-PROPHYLAXIS

#### Primary

To determine the comparative clinical effectiveness (absolute difference in the rate of PTS within the first 2 weeks post-TBI) of a 7-day course of phenytoin or levetiracetam, used as seizure prophylaxis, versus no AED for TBI patients.

#### Secondary

- Compare outcomes between the three arms
  - extended Glasgow Outcome Scale
  - cognitive function
  - quality of life (EQ-5D-5L)
  - Liverpool Adverse Events Profile
- To compare adverse events between the three arms
- To compare the frequency of PTS between the three arms
- Compare the PTS rate between phenytoin and levetiracetam
- Undertake a detailed economic evaluation.

## 8.5.2 MAST-DURATION

#### Primary

To determine the comparative clinical effectiveness (absolute difference in the rate of late PTS within 24 months post-TBI) of a longer course of phenytoin or levetiracetam (at least 6 months) versus a shorter course (up to 3 months) for TBI patients with early seizures (within first 7 days following trauma).

#### Secondary

- Compare outcomes between the two arms
  - extended Glasgow Outcome Scale
  - cognitive function
  - quality of life (EQ-5D-5L)
  - Liverpool Adverse Events Profile
- To compare adverse events between the two arms
- To compare the frequency of PTS between the two arms
- Undertake a detailed economic evaluation.

## Definition of a seizure

If a participant has a seizure they should contact their treating team. The participant should then be reviewed by a clinician to confirm whether a seizure has taken place. Participants will also be asked to report any seizures to the central coordination team. The GP will be sent a form asking them to confirm that a seizure has been clinically confirmed.

For study purposes, confirmed seizures will include any of the following:

1. Simple partial seizures:

- with motor symptoms: focal motor movements, versive/postural movements
- with sensory symptoms: olfactory sensations
- with autonomic signs
- with psychic symptoms (e.g. déjà vu, jamais vu)

2. Complex partial seizures:

- with impairment of consciousness only
- with impairment of consciousness plus automatisms (lip smacking, fumbling, etc.)

3. Partial seizures with secondarily generalized seizures;

- Unconsciousness with generalised clonic movements
- Unconsciousness with generalised tonic spasm, without clonic movements
- Unconsciousness or staring with one of the following preceding symptoms perceived by the participant:
  - A rising feeling from the abdomen to the throat
  - Smelling of odd scents
  - Stiffening or convulsions in the face or limb(s)
  - Turning the head to one side.

Excluded attacks are those deemed by the treating physician not to be epileptic seizures.

If performed as part of routine clinical care, electroencephalographic findings will be used as adjunct criteria in making a diagnosis of seizures.

During the period when participants are in-patients, it is anticipated that the occurrence of seizures will be confirmed by local clinical staff as per routine clinical practice. After discharge from hospital, participants and carers will be given a leaflets and have access to a video to allow them to recognise subtle manifestations of seizures.

#### 8.6 Trial Outcome Measures

#### 8.6.1 Primary outcome measure

**MAST-PROPHYLAXIS:** Occurrence of an acute symptomatic seizure within 2 weeks post-TBI. **MAST-DURATION:** Occurrence of late PTS within 24 months post-TBI

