Procedures for safety monitoring during trial	All results will be forwarded to the Data Monitoring Committee (DMC) who will address safety issues. Any significant adverse results will be reported to the DMC via the Trial Coordinating Centre (CCTU). Onward reporting to the TSC and Sponsor.				
Criteria for withdrawal of participants	
 
SUSAR
 
Withdrawal from treatment - participants may voluntarily withdraw from treatment for any reason at any time, but continue to provide follow-up data
 
Withdrawal from trial - participants may voluntarily withdraw from treatment for any reason at any time, and also withdraw from data collection
 
Patients will be withdrawn at any time if the investigator concludes that it would be in the patient's best interest for any reason
 
				
Randomisation	Randomisation in MAST-PROPHYLAXIS will occur within 48 hours from admission to NSU. Randomisation in MAST-DURATION can occur at any time point during acute hospitalisation in the NSU as long as the patient has been started on Phenytoin or Levetiracetam due to post-traumatic seizures.				

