# 6 Introduction

# 6.1 Background

Traumatic brain injury (TBI) is an alteration in brain function or other evidence of brain pathology, caused by an external force .It is a major public health problem that can result in physical, cognitive, functional and psychosocial disability . The majority of patients who have a TBI do not need to stay in hospital. However, approximately 9,000 patients require admission to a specialist hospital each year in the UK, as their injury is more serious . Post-traumatic seizures (PTS) are well recognised following TBI . They are classified as acute symptomatic or provoked (within 7 days post-TBI) or late (after 7 days). Seizures during acute hospitalisation can lead to significant derangement of brain physiology and can even lead to brain herniation and death. Additionally, PTS during acute hospitalisation have been shown to be an independent risk factor for PTS within 12 and 24 months following TBI . Late PTS within 24 months can have a negative impact on quality of life, return to work, return to driving, and can even result in death.

Current international guidelines for traumatic brain injury (TBI)  recommend the use of phenytoin for the prevention of early PTS when the benefits are thought to outweigh the risks, however the inadequacy of current evidence underpins this guidance. In practice alternative antiepileptic drugs (AEDs) such as levetiracetam and valproate are being used clinically as they are believed to have a more favourable risk profile. This is despite there being insufficient evidence to support their efficacy, or indeed that of phenytoin. In fact at the moment it remains unclear which AED treatment is more appropriate in patients with PTS and for how long patients should be treated. It is also unclear if prophylaxis for PTS following TBI is clinically effective, which patients might benefit from this treatment and for how long the drug should be given. The only evidence currently available dates back to 1990 when Temkin et al. showed a reduced incidence of rate of early seizures from 14.2% to 3.6% after administration of phenytoin .

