# 9.2 Exclusion Criteria

# MAST-PROPHYLAXIS:

The presence of any of the following will preclude patient inclusion:

- Post-traumatic seizures
- Unsurvivable injury
- Previous history of epilepsy
- Patients who are taking an AED pre-TBI
- Pregnancy or breastfeeding
- Any known hypersensitivity to study drugs (or hydantoins or pyrrolidone derivatives) or any of its excipients
- Time interval from the time of admission to NSU to randomisation exceeds 48 hours

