# MAST-DURATION:

The presence of any of the following will preclude patient inclusion:

- Unsurvivable injury
- Previous history of epilepsy
- Patients who are taking an AED pre-TBI
- Patient who has been clinically prescribed an AED to treat PTS (other than phenytoin or levetiracetam since current admission
- Any known hypersensitivity to study drug selected or any of its excipients
- For phenytoin: known hypersensitivity to other hydantoins
- For levetiracetam: known hypersensitivity to other pyrrolidone derivatives

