## 11.5 Trial assessments

## 11.5.1 Timing of assessments

Patients will be monitored as per routine clinical practice in the Neurosurgical Unit until discharge and thereafter at 6 months, 12 months, 18 months and 24 months (+/- 8 weeks at each time point) in both studies to score clinical outcome. Patients in the MAST-PROPHYLAXIS study will also be followed up at 14 days. Patients from the MAST-PROPHYLAXIS study may also be followed up at 60 months, subject to additional funding (+/- 8 weeks).

11.5.2 Assessments at time point

- Adverse events of special interest review during treatment.
- Assessment for seizures during hospital admission, at discharge at day 14 (by telephone if patient is already discharged) (PROPHYLAXIS only)
- EQ-5D-5L questionnaire at discharge

Follow up postal questionnaire/email/telephone call at 6 months (+/- 8 weeks), 12 months (+/- 8 weeks), 18 months (+/- 8 weeks), 24 months (+/- 8 weeks) post randomisation
 To document:

Occurrence of seizures

- GOSE questionnaire
- NSI questionnaire
- EQ-5D-5L questionnaire
- Liverpool Adverse Events Profile questionnaire

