#### 14.1.3 PTS recurrence

PTS recurrence will be measured from the date of randomisation to the 24 month follow up and will be reported for all causes.

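### The protocol uses two unreconciled start points for post-traumatic seizures, and the DURATION primary outcome read literally counts late seizures that precede randomisation

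*Protocol*

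**What the plan says.** **DURATION outcome.** Section 8.6.1 gives the primary outcome as "Occurrence of late PTS within 24 months post-TBI". The synopsis and section 8.5.2 use the same injury-based clock. Section 6.1 sets the boundary between early and late: "They are classified as acute symptomatic or provoked (within 7 days post-TBI) or late (after 7 days".

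**DURATION entry.** The synopsis states "Randomisation in MAST-DURATION can occur at any time point during acute hospitalisation in the NSU", provided that phenytoin or levetiracetam has been started for seizures. Sections 9.1 and 9.2 set no limit on the time from injury to randomisation. The exclusion closest to the point, "Patient who has been clinically prescribed an AED to treat PTS (other than phenytoin or levetiracetam since current admission", concerns which drug was given and not when a seizure occurred.

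**The other clock.** Section 14.1.3, under the response criteria, says "PTS recurrence will be measured from the date of randomisation to the 24 month follow up". Section 11.5.2 times the last contact at "24 months (+/- 8 weeks) post randomisation".

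**PROPHYLAXIS.** The primary outcome is "Occurrence of an acute symptomatic seizure within 2 weeks post-TBI". The only timing exclusion in section 9.2 is "Time interval from the time of admission to NSU to randomisation exceeds 48 hours". No limit runs from injury to admission.

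**The concern.** Take a DURATION patient with a further seizure on day 10 who is randomised on day 20. Under 8.6.1 this patient has met the primary outcome ten days before allocation. Under 14.1.3 the seizure does not count. The DURATION schedule in section 11.6 records seizures at the baseline visit, but no rule separates those from outcome events.

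A seizure before allocation cannot respond to the length of the course that follows. Counting it adds the same expected number of events to both arms, shrinks the absolute difference and costs power. The trial is also open label, so which seizures are primary events should be settled before anyone has outcome data to look at.

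The end of the window has the same fault. It closes 24 months after injury in 8.6.1, while 14.1.3 runs to a follow-up contact that is timed from randomisation with an 8-week margin.

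**Working it through.** **Inputs (protocol 16.1, 16.3).** DURATION: 25% v 12%, 188 observations per arm, two-sided 5%, stated power 90%. PROPHYLAXIS: 11% v 4%, 358 per arm, 2.7% threshold, stated power 91% for a single comparison.

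**Formula.** Power = Φ[(d − z·SE0)/SE1], where d is the difference, SE0 = √(2·p̄(1−p̄)/n) and SE1 = √((p1(1−p1)+p2(1−p2))/n).

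**Planned DURATION figure.** p̄ = 0.185, SE0 = 0.0401, SE1 = 0.0395. (0.13 − 1.96 × 0.0401)/0.0395 = 1.30, so power is 90.4%. The stated 90% reproduces and is not in dispute.

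**Dilution.** Section 16.3 does not say whether 25% and 12% run from injury or from randomisation, so both readings are shown. The shares are assumptions.

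*Reading A: the planned rates apply after randomisation, and a share f of patients in each arm is already an event.* Control = f + (1−f) × 0.25; long course = f + (1−f) × 0.12.

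| f | Control | Long course | Difference | Power |
|---|---|---|---|---|
| 0 | 25.0% | 12.0% | 13.0 | 90.4% |
| 2% | 26.5% | 13.8% | 12.7 | 87.2% |
| 5% | 28.8% | 16.4% | 12.4 | 82.0% |
| 10% | 32.5% | 20.8% | 11.7 | 72.9% |

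*Reading B: the 25% already includes x points of pre-randomisation events, and the planned ratio 12/25 = 0.48 acts only on the rest.* Long course = x + (0.25 − x) × 0.48.

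| x | Control | Long course | Difference | Power |
|---|---|---|---|---|
| 2 points | 25% | 13.0% | 12.0 | 84.3% |
| 3 points | 25% | 13.6% | 11.4 | 80.5% |
| 5 points | 25% | 14.6% | 10.4 | 71.7% |

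**PROPHYLAXIS window.** Days left at randomisation = 14 − (days from injury to admission) − (0 to 2). Same-day admission leaves 12–14 days, day 5 leaves 7–9, day 7 leaves 5–7 and day 12 leaves 0–2. The window has expired only if randomisation falls more than 14 days after injury, which means admission more than 12 days after it. If an assumed 5% or 10% of patients had expired windows and hence no events, the rates become 10.45% v 3.8% or 9.9% v 3.6%. Per-comparison power then goes from 91.2% to 89.6% or 87.6%.

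**The case against.** Section 14 is the part of the protocol that defines how outcomes are evaluated, and 14.1.3 counts from randomisation. A reader might infer from 8.6.1 that the trial definitely counts pre-randomisation seizures. The documents do not support that, because two rules stand and neither is given precedence. But 14.1.3 does not settle the matter either. It speaks of recurrence without naming a trial or the primary outcome, whereas 8.6.1 is the primary outcome section.

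A reader might also infer biased results. That does not follow. The events precede allocation, so randomisation balances them in expectation, and they neither favour an arm nor inflate type I error.

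The size is open to challenge. Five of 25 points would mean that one in five control-arm events over 24 months fell between day 8 and randomisation, in patients already on an anti-epileptic drug. Nothing in the protocol supports or excludes that share. Section 16.2 also provides for an interim review of sample size that allows for uncertainty in the 25% rate. That review is optional and would not settle which seizures count.

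For PROPHYLAXIS it is tempting to claim the same fault. It does not carry over. A prior post-traumatic seizure bars entry, so no event before allocation can count. An expired window needs a very late admission. The text permits this, and chronic subdural haematoma is a listed lesion type in 16.1, but no frequency is given. A two-week period from injury is a coherent clinical question.

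**Conclusion.** The DURATION point stands as a defect of definition. The injury-based outcome, the open-ended time of randomisation and the absence of a relevant exclusion together admit primary events that precede allocation, and 14.1.3 contradicts that count. The same patient can be an event under one section and not under the other.

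The harm is dilution and an unclear estimand. Its size rests wholly on an assumed share of affected patients. Over the ranges above, DURATION power lies between about 87% and 72% instead of 90%. If pre-randomisation late seizures are rarer than 2%, the loss is smaller.

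The PROPHYLAXIS point is minor: late admissions have a shortened and rarely an expired window, at a cost of about 2 to 4 points of power if 5–10% of windows had expired.

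**What to change.** **DURATION.** Define the primary outcome as a post-traumatic seizure occurring after both day 7 from injury and randomisation, classified by the date of the seizure and not of the contact, up to one stated 24-month end point. Record a late seizure before randomisation as a baseline characteristic. Use the same wording in 8.5.2, 8.6.1 and 14.1.3. Keep the injury-anchored version as a sensitivity analysis.

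**PROPHYLAXIS.** Keep the injury-anchored primary outcome and add a sensitivity analysis that counts 14 days from randomisation.

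**Cost.** This is mainly a wording amendment. If 25% and 12% describe the period after randomisation, DURATION keeps 90.4% power and its sample size. If they include earlier events, the observed rate may be slightly lower than planned. Dates of injury and of the baseline seizure are already in CRF part 1 (11.4). The follow-up list in 11.5.2 mentions only occurrence, so seizure dates must be captured there if they are not already.

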#### 8.6.2 Secondary outcome measures (both trials)

- Occurrence and time to PTS within 24 months post-TBI (MAST-PROPHYLAXIS ONLY)
- Extended Glasgow Outcome Scale, Neurobehavioral Symptom Inventory, quality of life (EQ-5D-5L), and Liverpool Adverse Events Profile at 6, 12, 18 and 24 months.
- Economic evaluation
- Frequency of PTS
- Mortality at 6, 12, 18 and 24 months.
- Adverse events of special interest during treatment.

#### 9 Selection and withdrawal of participants

## 9.1 Inclusion Criteria

## MAST-PROPHYLAXIS:

- Patients aged ≥10 years, with TBI managed in an NSU without an acute symptomatic seizure
- Patient or Legal Representative is willing and able to provide informed consent or in the absence of a legal representative, an Independent Healthcare Professional provides authorisation for patient randomisation within 48 hours of admittance.

# MAST-DURATION:

- Patients aged ≥10 years with TBI managed in an NSU who have started on an phenytoin or levetiracetam due to an acute symptomatic seizure during acute hospitalisation
- Patient or Legal Representative is willing and able to provide informed consent or in the absence of a legal representative, an Independent Healthcare Professional provides authorisation for patient enrolment

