## MAST-DURATION:

P Patients aged ≥10 admitted to the NSU who have been started on an AED (phenytoin or levetiracetam accepted), due to early symptomatic seizures after TBI (within first 7 days following trauma).

I The intervention is an AED administered for at least six months

C The comparator is an AED administered for up to 3 months

O Outcome is evidence of PTS at 2 years from TBI

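### MAST-DURATION states its index-seizure window and the start of its primary-outcome clock inconsistently, so a late seizure before randomisation could count as a primary event

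*Protocol*

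**What the plan says.** **Population.** Section 8.5.2 sets the primary objective "for TBI patients with early seizures (within first 7 days following trauma"), and section 8.1 uses the same limit. The population statement in section 7 describes patients started on a drug "due to early symptomatic seizures after TBI (within first 7 days following trauma").

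**Eligibility.** Section 9.1 admits patients started on phenytoin or levetiracetam "due to an acute symptomatic seizure during acute hospitalisation", and the synopsis eligibility text matches it. Neither gives a number of days, and no exclusion in section 9.2 refers to the timing of the seizure.

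**Randomisation.** The synopsis row says "Randomisation in MAST-DURATION can occur at any time point during acute hospitalisation in the NSU". The one condition it attaches reads "as long as the patient has been started on Phenytoin or Levetiracetam due to post-traumatic seizures". Here the seizure is qualified neither as early nor as acute symptomatic.

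**Terms.** Section 6.1 sorts post-traumatic seizures into two classes: "acute symptomatic or provoked (within 7 days post-TBI) or late (after 7 days"). Section 8.6.1 words the MAST-PROPHYLAXIS primary outcome as "Occurrence of an acute symptomatic seizure within 2 weeks post-TBI", which takes the first term past day 7.

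**Outcome clock.** Section 8.6.1 defines the MAST-DURATION primary outcome as late seizures up to 24 months, timed from the injury. Section 14.1.3 measures seizure recurrence from the date of randomisation. No section says whether late seizures before randomisation count towards the primary outcome.

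**The concern.** There are two linked problems.

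First, the 7-day limit appears in the statements of aim and design but not in words in the criterion that sites apply. It is reached only through a term defined in the Background and used differently in the outcome section. Two sites could decide differently about the same patient.

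Second, the primary outcome can overlap with the time before randomisation. A patient with a qualifying seizure on, say, day 3 may still be in the unit on day 12, seize again, and be randomised on day 13. All of that is allowed. Under section 8.6.1 the day-12 seizure is a late seizure within 24 months of injury, so the patient is an event whichever duration is allocated. Such events fall equally, on average, in both arms. They do not favour either arm, but they shrink the absolute difference that the trial is sized to detect. Under section 14.1.3 the same seizure would not count.

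**Working it through.** **Step 1. Compare the wording.**

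| Place in protocol | Index seizure | Day limit |
|---|---|---|
| Sections 7, 8.1, 8.5.2 | early | first 7 days, explicit |
| Section 9.1 and synopsis eligibility | acute symptomatic, during acute hospitalisation | only through the definition in 6.1 |
| Synopsis randomisation row | any post-traumatic seizure | none |
| Section 8.6.1 (MAST-PROPHYLAXIS outcome) | acute symptomatic | used up to 2 weeks |

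| Place in protocol | What is counted | Counted from |
|---|---|---|
| Section 8.6.1 | late seizures to 24 months | injury |
| Section 14.1.3 | seizure recurrence to 24 months | randomisation |

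The seizure that tests the second table falls after day 7 and before randomisation. It counts in the first row and not in the second.

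**Step 2. Reproduce the plan's figures.** Inputs from sections 16.1 and 16.3: 25% against 12%, two-sided 5%, 90% power, 188 observed per arm, 12% drop-out, 428 recruited. With the pooled-variance formula for two proportions,

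power = Φ{ [d√n − 1.96√(2p̄(1−p̄))] / √(p₁(1−p₁) + p₂(1−p₂)) },

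where d = 0.13, p̄ = 0.185 and n = 188:

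- numerator: 0.13 × 13.711 − 1.96 × 0.5491 = 1.782 − 1.076 = 0.706
- denominator: √(0.1875 + 0.1056) = 0.5414
- power: Φ(1.304) = 90.4%

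The same formula needs 186 per arm for 90% power. Recruitment is 376 / 0.88 = 427.3, rounded up to 428. The plan's figures stand.

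**Step 3. Effect if late seizures before randomisation count.** Let f be the share of patients with such a seizure. The protocol does not give f, so the values below are assumptions. If the planned rates hold in everyone else, each arm's rate becomes f + (1 − f)p and the difference becomes (1 − f) × 13 points.

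| f (assumed) | Control | Longer course | Difference (points) | Power at 188 per arm | Total to recruit for 90% |
|---|---|---|---|---|---|
| 0 | 25.0% | 12.0% | 13.0 | 90.4% | 423 |
| 2% | 26.5% | 13.8% | 12.7 | 87.2% | 471 |
| 5% | 28.8% | 16.4% | 12.4 | 82.0% | 544 |
| 10% | 32.5% | 20.8% | 11.7 | 72.9% | 680 |

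The last column is twice the required number per arm (186, 207, 239, 299) divided by 0.88, rounded up. The first row is 423 rather than 428 because the plan uses 188 per arm where 186 suffice.

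**Step 4. Alternative handling.** If these patients were left out, n per arm would be 188(1 − f) at the planned rates, and power would be 89.8%, 88.9% and 87.2% for f of 2%, 5% and 10%. Section 16.1 includes all randomised participants, so this is only a comparison.

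**The case against.** A reader might infer something stronger: that section 9.1 omits the 7-day limit, so a patient whose first seizure is on day 10 can enter having already met the primary endpoint. The protocol does not support that. Section 6.1 makes acute symptomatic and late mutually exclusive, split at day 7. If that split is applied throughout, a first seizure on day 10 is late and fails 9.1. If acute symptomatic is stretched to 2 weeks, late would start after 2 weeks and day 10 is not an outcome event. The claim needs both boundaries at once.

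Other points also weigh against the stronger reading. The 2-week wording belongs to the other trial, whose outcome the synopsis gives simply as seizures within 2 weeks. The synopsis randomisation row concerns timing, and section 9.3 randomises only patients who meet the eligibility criteria. The synopsis purpose row makes entry to either trial depend on whether an early seizure has occurred. Section 7 speaks of preventing further seizures, which fits counting from randomisation.

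These points stand: the limit is implicit in 9.1, not absent. They do not settle the outcome clock. Section 14.1.3 concerns recurrence and does not say that it governs the primary outcome, which 8.6.1 times from injury. The section 11.6 schedule records seizures at baseline as well as at follow-up. The route through a second seizure after day 7 needs no stretching of any term, because that patient is eligible under the strictest reading.

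**Conclusion.** The point holds as an inconsistency in two places. The index-seizure window is explicit in sections 7, 8.1 and 8.5.2, implicit in 9.1 and the synopsis eligibility text, and missing from the synopsis randomisation row. The primary-outcome clock starts at injury in 8.6.1, while 14.1.3 starts the recurrence clock at randomisation. Of the two, the clock matters more, because it decides whether a seizure that allocation cannot have affected is a primary event.

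The size of the effect cannot be derived from the protocol. The losses to about 87%, 82% and 73% power rest on three assumptions: the value of f, the planned rates holding in all other patients, and 8.6.1 being applied as written. If f is near zero the loss is negligible, though the contradiction remains. A reader might also take these figures to mean that the trial is undersized. They do not show that: 188 per arm, 428 in total and 90% power all reproduce.

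**What to change.** 1. State the index-seizure window in days in the section 9.1 inclusion criterion, the synopsis eligibility text and the synopsis randomisation row, reconciled with sections 6.1, 7, 8.1 and 8.5.2. Bring the use of acute symptomatic in 8.6.1 into line with its definition in 6.1.
2. Reconcile 8.6.1 with 14.1.3 by stating that only late seizures occurring after randomisation count towards the MAST-DURATION primary outcome. Counting then starts at the later of the end of day 7 and randomisation.

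The second change is needed as well as the first. A day limit on entry does not deal with a patient who qualifies by day 7 and seizes again before randomisation, and excluding only the seizure that led to entry would leave that second seizure countable. Affected patients stay in the intention-to-treat analysis; only the seizure before randomisation is not counted.

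The cost is a wording amendment. Section 11.4 already records the date of the seizure at baseline, and no stated sample size or power figure changes. The downside is that, with the 7-day limit written out, a few patients with later first seizures become clearly ineligible.
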